#### 5.7.2.2. Continuous Endpoints Anticipated to have a Non-normal Distribution

Continuous secondary efficacy variables defined in Section 4.7.2 and Section 4.7.3 anticipated to have a non-normal distribution (ie, TG) will be analyzed using the same MMRM model as described for the primary endpoint in TG.

For comparisons that defined on the DBTP-stable Arm 1 patients, the MMRM model will be fitted again to exclude the Arm 1 patients who do not meet the DBTP-stability criteria. The LS means will be back-transformed into the geometric means to ease clinical interpretation of the result. Table 7 summarizes the statistical analysis methods that will be performed for the secondary efficacy variables in fasting TG.

Table 7. Summary of Statistical Estimates, Comparisons, and Descriptive Statistics in Fasting-TG Secondary Endpoints

Endpoints	Cohort		Estimates	Statistics
• Percent change in fasting TG from baseline to week 12.	fo B Co	eparately or Cohort and ohort +B	Baseline adjusted least-squares (LS) means estimates at week 12 for each treatment subgroup with their corresponding standard errors and 95% confidence intervals. The LS means at week 12 will be back-transformed into the geometric means.	Difference of the study treatment TG geometric mean changes from baseline to week 12 will be provided along with its corresponding 95% confidence interval, and nominal p-value.
• Percent change in fasting TG from baseline to week 24	fo A, B, Co	eparately or Cohort , Cohort , and ohort +B	N/A	For Arm 2 patients, descriptive summaries will be provided at each protocol specified visit up to week 24; median percent changes with Q1 and Q3 bars will be plotted across visits; a spaghetti plot will be provided for individual patient data across visits.

Protocol: R4461-PLD-20100

 
Percent change in fasting TG from baseline to week 12
 
Percent change in fasting TG from week 12 to week 24
 
	• Separately for Cohort A, Cohort B, and Cohort A+B	For Arm 1, baseline adjusted least-squares (LS) means estimates at week 12 and week 12 adjusted least-squares (LS) means estimates at week 24 will be provided with the corresponding standard errors and 95% confidence intervals. The LS means will be back-transformed into the geometric means.	For Arm 1, difference between the fasting TG geometric means from week 12 to week 24 and from baseline to week 12 will be provided along with its corresponding 95% confidence interval, and nominal p-value when appropriate.

 
Percent change in fasting TG from baseline to week 12
 
Percent change in fasting TG from week 12 to week 24
 
	• Separately for Cohort A, Cohort B, and Cohort A+B	N/A	Fasting TG median change from REGN4461 Day 1 to REGN4461 week 12 for combined Arm 1 and Arm 2 patients will be provided along with Q1 and Q3 bars.

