4.2. Secondary Endpoints

Note: Patients in study arm 1 must meet stability criteria during TP1 (a change in $HbA1c \le 0.5$ percentage points and a change in $TG \le 25\%$) to be included for specific endpoints as indicated below.

The following secondary endpoints will be analyzed for cohort B and for the combined set of cohorts A plus B:

- Percent change in fasting serum TG from baseline to week 12 in patients with elevated baseline fasting TG (>200 mg/dL)
- Absolute change in HbA1c from baseline to week 12 in patients with elevated baseline HbA1c (>7.0%)

The following secondary endpoints will be analyzed for cohorts A and B separately, and for the combined set of cohorts A plus B:

- Percent change in fasting serum TG from baseline to week 12 compared to the percent change between week 12 and week 24 (study arm 1)
- Percent change in fasting serum TG from baseline to week 24 (study arm 2)
- Percent change in fasting serum TG after the first 12 weeks of exposure to REGN4461— from baseline to week 12 (study arm 2) and from week 12 to week 24 (study arm 1; patients must meet stability criteria)
- Change in HbA1c from baseline to week 12 compared to the change between week 12 and week 24 (study arm 1)
- Change in fasting glucose from baseline to week 12 compared to the change between week 12 and week 24 (study arm 1)
- Change in HbA1c from baseline to week 24 (study arm 2)
- Change in fasting glucose from baseline to week 24 (study arm 2)
- Change in HbA1c from baseline to week 12 (study arm 2) and from week 12 to week 24 (study arm 1; patients must meet stability criteria)
- Change in fasting glucose from baseline to week 12 (study arm 2) and from week 12 to week 24 (study arm 1)

- Percent change in liver fat (MRI-PDFF) from baseline to week 12, REGN4461 versus placebo in patients with baseline liver fat (MRI-PDFF) ≥8.5%.
- Percent change in liver fat (MRI-PDFF) from baseline to week 12 compared to the percent change between week 12 and week 24 (study arm 1) in patients with baseline liver fat (MRI-PDFF) ≥8.5%.
- Percent change in liver fat (MRI-PDFF) from baseline to week 24 (study arm 2) in patients with baseline liver fat (MRI-PDFF) ≥8.5%.
- Percent change in liver fat (MRI-PDFF) from baseline to week 12 (study arm 2) and from week 12 to week 24 (study arm 1) in patients with baseline liver fat (MRI-PDFF) ≥8.5%.
- Change on the daily lipodystrophy hunger questionnaire from baseline to week 12 and week 24

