Baseline testing occurs in the screening period and the placebo run-in period (see Table 1). After baseline testing, patients in each cohort will be randomized 1:1 to study arm 1 (placebo in TP1 and REGN4461 in TP2) or study arm 2 (REGN4461 in TP1 and TP2), and stratified based on screening HbA1c (HbA1c \leq 7.0% or HbA1c \geq 7.0%) within each cohort.

On day 1, the first dose will be administered IV (mg/kg REGN4461 or placebo) and patients will be observed for at least 4 hours. Starting on day 8, patients will receive matched volumes of SC administered REGN4461 (mg QW) or placebo, respectively, once weekly for a total of 11 SC doses. Fasting blood draws will be taken every 2 weeks according to Table 2.

During the final 2 weeks of TP1, fasting blood draws will be performed weekly (weeks 10, 11, 12). The mean (geometric for TG and arithmetic for all other measures) of these 3 measurements will be taken as the end measure of TP1 and beginning measurement for TP2. Bioimpedance will be assessed during a mandatory in-clinic study visit (week 12). At the end of TP1, patients will undergo liver MRI and whole-body DXA.

12-week single-blind treatment period (TP2); Day 85 until week 24

On day 85 (week 12), patients will receive double-blind dosing in order to maintain blinding to study arm assignment and will then be observed for at least 4 hours:

- Study arm 1: IV loading dose of REGN4461 (mg/kg) followed by SC placebo;
- Study arm 2: placebo IV infusion followed by SC REGN4461 (mg).

Starting at week 13, REGN4461 (mg SC QW) will be administered in a single-blind manner to patients in both study arms (patient remains blinded to treatment allocation). Fasting TG and glucose measurements will occur every 2 weeks through week 20 (Table 2). During the final 2 weeks of TP2, fasting blood draws will be performed weekly (weeks 22, 23, 24). The mean (geometric for TG and arithmetic for all other measures) of these 3 measurements will be taken as the end measure of TP2. Bioimpedance will be assessed during the mandatory in-clinic visit (week 24). At week 24, patients will undergo liver MRI and whole-body DXA.

16-week off-drug safety follow-up period; Day 169 until week 40

This period will be used to monitor efficacy (glycemic, lipid parameters, daily lipodystrophy hunger patient reported outcome [PRO]), safety (hematology, chemistry, urinalysis, vital signs and AEs), PK and PD assessments as REGN4461serum concentrations decline.

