7.2.1. Inclusion Criteria

A patient must meet the following criteria to be eligible for inclusion in the study:

- 1. Male or female, ≥ 18 years of age at the screening visit.
- 2. Clinical diagnosis of familial partial lipodystrophy:
 - a) Altered body fat distribution including lipoatrophy at one or more sites, as determined by physical examination

AND

- b) Metabolic sequelae of partial lipodystrophy, as evidenced by a medical history of at least 1 of the following:
 - i) Fasting hypertriglyceridemia as evidence by multiple readings >150 mg/dL
 - ii) Diabetes as evidenced by American Diabetes Association criteria
 - iii) Hepatic steatosis as evidenced by liver ultrasound (Grade II-III) or MRI-PDFF (>5.6%)

AND EITHER (c) or (d)

c) History of known pathogenic mutation in an FPLD-related gene (Section 3.2.1) OR

3. Fasting leptin level ≤20.0 ng/mL

Note: Refer to Appendix 1 for actions based on leptin results.

- 4. Presence of significant metabolic abnormalities satisfying 1 of the following:
 - a) HbA1c >7.0% AND fasting TG >200 mg/dL

OR

b) Fasting TG >450 mg/dL

- 5. Stable body weight within the 3 months prior to screening (no gain or loss of >5% current weight)
- 6. Stable diet during the past 3 months defined as no major change in macronutrient composition (eg, starting or stopping diets such as Adkins, Paleo, Vegetarianism, Veganism).
- 7. No clinically meaningful change in diabetes medication regimen in the 3 months prior to screening (addition, subtraction, or change in dosing). Changes in insulin dosing within 3 months are allowed if the change is <30% of the total daily dose.
- 8. No clinically meaningful change (addition, subtraction, or dose change) in medications for hyperlipidemia taken by prescription or over the counter (including fish oil or niacin) for the past 3 months prior to screening.
- 9. Willing and able to comply with clinic visits and study-related procedures.

Note: patients incapable of completing COA assessments or unable to undergo MRI will not be excluded.

10. Provide informed consent signed by study patient or legally acceptable representative.

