11.4.3.2. Secondary Efficacy Analysis

For the secondary analysis, the change from baseline to week 12 will be compared to the change between week 12 and week 24 for study arm 1 to evaluate the treatment effect of REGN4461 on HbA1c and fasting TG.

For continuous secondary endpoints measured in the double-blind period, summary statistics, including the mean (or median) change from baseline, SE, 95% confidence interval, and nominal p-value when appropriate will be provided using the MMRM or ranked ANCOVA (fasting TG only). Descriptive statistics may be provided by subtype of PLD mutations.

For categorical secondary endpoints, appropriate tests, eg,: Fisher's exact test, will be used to evaluate the treatment effect.

In addition to the summary statistics described above, mean changes (\pm SE) will be plotted over time by the treatment group. A spaghetti plot will be provided for co-primary endpoints by the treatment group.

When combining patients from study arm 1 and study arm 2 for determining within-group effects after 12 weeks of REGN4461 treatment, patients in study arm 1 will only be included if they meet

stability criteria for TP1 (when they are receiving placebo). The stability criteria are a change in $HbA1c \le 0.5$ percentage points and a change in $TG \le 25\%$.

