#### 1.2.4. Modifications from the Statistical Section in the Final Protocol

The content of this SAP reflects the content of the statistical section of Protocol R4461-PLD-20100 Amendment 1 with the following exceptions:

- Protocol Section 4. Endpoints: The definitions of endpoints are clarified in SAP Section 5.7 by replacing:
  - "elevated baseline fasting TG" into "screening TG"
  - "elevated baseline HbA1c" for defining subgroup into "screening HbA1c" to match HbA1c strata (screening HbA1c ≤7.0%, >7.0%)
  - "baseline leptin" for defining Cohort into "screening leptin"
- Protocol Section 11.3.2. Safety Analysis Set: Safety analysis set (SAF) is replaced with DB SAF and SB SAF as follows in SAP Section 3.2:
  - DB SAF includes all randomized patients who received any double-blind study drug.
  - SB SAF includes all the patients in the double-blind SAF who also received at least 1 study drug in the single-blind treatment period.
- Protocol Section 11.4.5.4. Treatment Compliance: Compliance % calculation is replaced with study treatment administration interval compliance in SAP Section 5.8.8.
- Protocol Section 11.4.3. Efficacy Analyses: The randomization strata per IVRS in the analysis models (eg, MMRM) are replaced with actual strata in SAP Section 5.7 to reflect the actual disease characteristic for statistical modeling.
- Protocol Section 11.4.3. Efficacy Analyses: Due to the early termination of the study and subsequent limited number of participants enrolled, only descriptive summaries

Protocol: R4461-PLD-20100

and line plots for fasting TG, HbA1c, fasting glucose, liver fat (MRI-PDFF), and Daily Lipodystrophy Hunger Questionnaire (DLHQ) over time will be provided by treatment group. Spaghetti plots for fasting TG, HbA1c, fasting glucose, liver fat (MRI-PDFF), and DLHQ will be provided for individual patient data across visits for the endpoints by treatment group if applicable.

Protocol: R4461-PLD-20100

Date: May 16, 2024

• SAP Section 7 Timing of Statistical Analyses: First Step Analysis and Second Step Analysis will not be performed.

# 1.2.5. Revision History for Statistical Analysis Plan Version 1

This is the original version of the SAP.

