## 5.7.2. Analysis of Secondary Efficacy Variables

Statistical analyses for the secondary efficacy endpoints (defined in Section 4.7.2) and SBTP-specific secondary efficacy endpoints (described in Section 4.7.3) will be performed in the FAS population.

All measurements, scheduled or unscheduled, will be assigned to efficacy analysis windows defined in Appendix 10.2 in order to provide an assessment for these time points. For fasting TG, measurements on not-fasting patients will be excluded; the median percent changes (with Q1 and Q3 bars) will be plotted across visits by treatment group.

Multiple types of measurements are planned to be analyzed during differing time points in the trial, specifically continuous measurements expected to have a normal distribution (example: absolute change in HbA1c) and continuous measurements expected to have a non-normal distribution (example: TG).

The following patient groups are also used for analyzing secondary efficacy variables:

- Combined Cohort A+B include all patients in Cohort A and Cohort B as defined in Section 2.1.
- DBTP-stable patient is defined as a patient who meets both of the following two stability criteria:
  - Absolute change in HbA1c from baseline to week  $12 \le 0.5\%$
  - Percent change in fasting serum TG from baseline to week  $12 \le 25\%$

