# Table 5. Summary of Descriptive Statistics in Normally Distributed Secondary Endpoints based on REGN4461 Exposure

NOTE: Efficacy data for study treatment arm 1 (placebo) and arm 2 (REGN4461) will be combined by re-aligning to the first REGN4461 treatment administration, specifically study day 1 for arm 2 and week 12 for arm 1 will become REGN4461 Day 1. These descriptive statistics will be presented three times, specifically in Cohort A, Cohort B, and Cohort A+B.

Endpoints	Descriptive Statistic	
Absolute change in HbA1c from baseline to week 12	HbA1c mean changes from REGN4461     Day 1 to REGN4461 week 12 for combined DBTP-stable Arm 1 patients and Arm 2 patients will be provided along	

Regeneron Pharmaceuticals, Inc.

Page 38 of 88

Protocol: R4461-PLD-20100

• Absolute change in HbA1c from week 12 to week 24	with its corresponding 95% confidence interval.

 
Change in fasting glucose from baseline to week 12
 
Change in fasting glucose from week 12 to week 24
 
	• Fasting glucose mean changes from REGN4461 Day 1 to REGN4461 week 12 for combined Arm 1 and Arm 2 patients will be provided along with its corresponding 95% confidence interval.

 
Percent change in liver fat (MRI-PDFF) from baseline to week 12
 
Percent change in liver fat (MRI-PDFF) from week 12 to week 24
 
	• Liver fat (MRI-PDFF) mean changes from REGN4461 Day 1 to REGN4461 week 12 for combined Arm 1 and Arm 2 in patients with hepatic steatosis (baseline MRI-PDFF ≥8.5%) will be provided along with its corresponding 95% confidence interval.

Table 6. Summary of Statistics for Patients Randomized to Placebo in Normally distributed Secondary Endpoints

NOTE: These statistical estimates and descriptive statistics will be presented three times, specifically in Cohort A, Cohort B, and Cohort A+B.

Endpoints	Estimates	Comparison

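### SAP Table 7 omits the protocol's stability restriction on Arm 1 from the pooled fasting TG row, and SAP 1.2.4 does not list this as a departure

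*SAP*

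**What the plan says.** Protocol 4.2 lists a secondary fasting TG endpoint over the first 12 weeks of exposure. It combines Arm 2 from baseline to week 12 with Arm 1 "from week 12 to week 24 (study arm 1; patients must meet stability criteria"). The HbA1c endpoint carries the same condition. Protocol 11.4.3.2 states it generally: when the arms are combined for within-group effects, "patients in study arm 1 will only be included if they meet" the TP1 stability criteria. The criteria are an HbA1c change of at most 0.5 percentage points and a TG change of at most 25%.

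SAP 5.7.2 turns this into a named patient group: "DBTP-stable patient is defined as a patient who meets both of the following two stability criteria", with the same two limits. SAP Table 5 uses the group for the pooled HbA1c mean change, "for combined DBTP-stable Arm 1 patients and Arm 2 patients will be provided along" with a 95% confidence interval. The pooled fasting TG row, the last in SAP Table 7, reads "Fasting TG median change from REGN4461 Day 1 to REGN4461 week 12 for combined Arm 1 and Arm 2 patients will be provided", with Q1 and Q3. It has no stability qualifier, and its Estimates column is N/A.

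SAP 1.2.4 says the SAP follows the protocol's statistical section apart from a list of exceptions. Dropping the stability rule for pooled TG is not on that list.

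**The concern.** The two pooled results belong together: the same exposure period, the same arms, and the two metabolic measures that form the co-primary pair. The protocol puts the same entry condition on both. If the SAP is programmed as printed, HbA1c uses the stable Arm 1 patients and TG uses every Arm 1 patient with data. Nothing in the SAP tells the reader that the two rows rest on different patients, or that the TG row differs from its protocol definition.

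A related ambiguity should be settled in the same edit. The stability limits carry no absolute-value sign. Read literally, a placebo patient whose TG falls 60%, or whose HbA1c falls 2 points, counts as stable.

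**Working it through.** **Text comparison.**

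| Place | Pooled endpoint | Arm 1 patients admitted |
|---|---|---|
| Protocol 4.2 | fasting TG | stable only |
| Protocol 4.2 | HbA1c | stable only |
| Protocol 11.4.3.2 | any pooling of the two arms | stable only |
| SAP Table 5 | HbA1c | DBTP-stable only |
| SAP Table 7 | fasting TG | no restriction stated |
| SAP 1.2.4 | list of exceptions | not mentioned |

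For TG both protocol sections agree, so the SAP row departs from both. Pooled fasting glucose and liver fat in SAP Table 5 also lack the rule. That matches Protocol 4.2, which does not ask for it there, though not the general sentence in 11.4.3.2.

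**Plan's own figures.** The 90% half-width is t(0.95, 18) × SD × √(2/10), with t = 1.734.
- HbA1c: 1.734 × 1.81 × 0.447 = 1.40 (stated 1.4).
- Log TG: 1.734 × 0.87 × 0.447 = 0.675 (stated 0.67).

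Both reproduce when the stated SDs are used as SDs of the 12-week change, so they are used that way below.

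**Illustration: how many Arm 1 patients each rule keeps.**

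Inputs from the documents:
- 10 Arm 1 patients per cohort (Protocol 6.1.1).
- SDs of 0.87 (log TG) and 1.81 (HbA1c).
- Placebo change implied by the footnote to Protocol Table 3 and SAP Table 2. HbA1c: −1.18 − (−0.98) = −0.20. TG ratio: 0.48/0.53 = 0.906, log −0.099.

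Assumptions, not from the documents:
- Normal changes, with TG and HbA1c independent.
- As a second case, visit SDs of 0.3 (log TG) and 0.5 (HbA1c). Multiplied by √2 these give change SDs of 0.424 and 0.707.

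The TG limits on the log scale are ln 1.25 = 0.223 and ln 0.75 = −0.288.

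*Stated SDs.*
- TG, upper limit only: Φ((0.223 + 0.099)/0.87) = Φ(0.370) = 0.644.
- TG, both limits: 0.644 − Φ(−0.217) = 0.644 − 0.414 = 0.230.
- HbA1c, upper limit only: Φ((0.5 + 0.2)/1.81) = Φ(0.387) = 0.651.
- HbA1c, both limits: 0.651 − Φ(−0.166) = 0.651 − 0.434 = 0.216.
- Both criteria: one-sided 0.644 × 0.651 = 0.419; two-sided 0.230 × 0.216 = 0.050.

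*Smaller SDs.*
- TG: Φ(0.760) = 0.776; two-sided 0.776 − 0.328 = 0.448.
- HbA1c: Φ(0.990) = 0.839; two-sided 0.839 − 0.336 = 0.503.
- Both criteria: one-sided 0.651; two-sided 0.225.

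| Rule | Of 10 Arm 1 patients | Chance none qualifies (two-sided) |
|---|---|---|
| Table 7 as written | 10 | – |
| One-sided limits | 4.2 to 6.5 | – |
| Two-sided limits | 0.5 to 2.3 | (1 − 0.050)^10 = 0.60 to (1 − 0.225)^10 = 0.08 |

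These are patient counts. They say nothing about how far the pooled TG median would move.

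**The case against.** The strongest reply is that the SAP did intend the rule for TG. The text just above Table 7 says that, for comparisons defined on DBTP-stable Arm 1 patients, the MMRM will be refitted without the Arm 1 patients who are not stable. SAP 1.2.4 also keeps the protocol in force except for listed items, so the protocol's condition arguably still governs. This stands as evidence of a dropped word. It does not repair the row: the sentence concerns an MMRM refit, the pooled TG row is a median with no model estimate, and no other Table 7 row is defined on stable patients.

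A reader might infer that the sponsor chose to relax the rule for TG. The documents do not support that; the orphaned refit sentence points the other way.

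A reader might also infer that the unsigned limits are a SAP departure. They are not. Protocol 4.2 and 11.4.3.2 print them the same way, so both documents share the ambiguity. A magnitude was probably meant: elsewhere the protocol treats stability as two-sided, "Stable body weight within the 3 months prior to screening (no gain or loss of >5% current weight"). That is a body-weight criterion and only an analogy. The SAP's term absolute change does not settle it, because SAP 4.7.1 uses the term to name the HbA1c endpoint as opposed to a percent change.

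Finally, the row may not be produced. SAP 1.2.4 says: "Due to the early termination of the study and subsequent limited number of participants enrolled, only descriptive summaries" and line plots over time will be given by treatment group. A summary that combines both arms does not fit that description easily. SAP 1.2.4 does not withdraw Table 7 by name, however, so the row still stands in the plan.

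**Conclusion.** The inconsistency holds on the text alone and needs no assumption. The protocol restricts pooled TG to stable Arm 1 patients, the SAP row does not, and the change is not listed. It alters which patients form a protocol-listed secondary result.

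The point is minor. The row is descriptive, no formal hypothesis is tested, and no primary conclusion is affected. A reader might infer that the pooled TG effect is biased by a known amount. The documents give no basis for a size or a direction.

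The counts (10, against about 4.2 to 6.5 or 0.5 to 2.3) are an illustration at planned size. They rest on normality, independence of TG and HbA1c changes, the implied placebo change, and SDs that are partly assumed. They also treat the end of TP1 as a single visit, whereas Protocol 6.1 averages the late visits: "The mean (geometric for TG and arithmetic for all other measures) of these 3 measurements will be taken as the end measure of TP1". Averaging would tend to keep more patients. Actual enrolment after early termination is not given.

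**What to change.** Add the DBTP-stable qualifier for Arm 1 to the pooled fasting TG row of SAP Table 7, in the form Table 5 uses for HbA1c. If the unrestricted pool is intended, list it in SAP 1.2.4 as a departure from Protocol 4.2 and 11.4.3.2, with the reason.

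In the same edit, write the limits in SAP 5.7.2 as |HbA1c change| ≤ 0.5 percentage points and |TG percent change| ≤ 25%, and note that this clarifies wording shared with the protocol.

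The cost is one qualifier or one listed exception, plus two definition lines. The real downside is that the two-sided stable set may be nearly empty in a cohort, and smaller still after early termination. Report the number of Arm 1 patients beside each pooled result so that a reader can see this.
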